14.2 Apache II Score

-					1				
Parameter/points	4	3	2	1	0	1	2	3	4
Core temperature	≥41	39–40.9		38.5–38.9	36–38.4	34–35.9	32–33.9	30–31.9	≤29.9
Mean art. pressure (mmHg)	≥160	130–159	110–129		70–109		50–69		≤49
Heart rate (/min)	≥180	140–179	110–139		70–109		55–69	40–54	≤39
Respiratory rate (/min) Spontaneous or ventilated	≥50	35–49		25–34	12–24	10–11	6–9		≤5
Oxygenation (mmHg) a) FiO ₂ ≥0,5: AaDO ₂ b) FiO ₂ <0,5: PaO ₂	≥500	350–499	200–349		<200 >70	61–70		55–60	<55
Arterial pH	≥7.7	7.6–7.69		7.5–7.59	7.33–7.49		7.25-7.32	7.15–7.24	<7.15
Natrium (mmol/l)	≥180	160–179	155–159	150–154	130–149		120–129	110–119	<110
Kalium (mmol/l)	≥7	6–6.9		5.5–5.9	3.5-5.4	3–3.4	2.5–2.9		<2.5
Creatinine (mg/dl) ¹	≥3,5	2-3.4	1.5–1.9		0.6–1.4		<0.6		
Hematocrite (%)	≥60		50-59.9	46-49.9	30–45.9		20-29.9		<20
Leucocytes (10 ³ /mm ³)	≥40		20-39.9	15–19.9	3–14.9		1–2.9		<1
Glasgow Coma Scale ²				Sc	ore=15 minu	s GCS			
Venous HCO ₃ (mmol/l) ³	≥52	41–51.9		32–40.9	22–31.9		18–21.9	15–17.9	<15

¹ In case of acute renal failure ×2

- The following points are assigned according to age: <=42 years: 0; 45 54 years: 2; 55 64 years: 3; 65 74 Jahre: 5; >=75 years: 6
- The following data about chronic diseases are collected (yes/no):

Liver: Cirrhosis (biopsy) and proven portal hypertension or gastrointestinal

haemorrhage caused by portal hypertension or previous episodes of liver

failure, encephalopathy, coma

Cardiovascular: NYHA IV

Respiratory: Chronic, restrictive, obstructive or vascular diseases that cause serious

disability (for example, inability to climb stairs or do household chores); proven chronic hypoxia, hypercapnia, secondary polycythemia, severe

pulmonary hypertension (> 40 mmHg), need for ventilation

Renal: Need for chronic dialysis

Immunsuppresive: Therapies that reduce resistance to infections (e.g., immune suppression,

chemotherapy, radiation, long-term treatment (up to 30 days prior to hospitalization), or treatment with high-dose steroids (> 16mg / kg for 5 days)); the presence of a disease that has progressed so far that the immune system is severely impaired (e.g. leukemia, lymphoma, AIDS)

- 0 points, if the answer to all five questions is "no"
- 2 points, if the answer to at least one question is "yes" and the patient is in an elective post-operative state
- 5 points, if the answer to at least one question is "yes" and the patient is in a postoperative emergency or has not undergone surgery

Reference: Knaus WA, Draper EA, Wagner DP, Zimmerman JE. APACHE II: a severity of disease classification system. Crit Care Med 1985;13(10):818–829.

² see page 58

³ only when arterial blood gases are missing

14.3 New Simplified Acute Physiology Score (SAPS II)

Parameter	Befund	Punktwert
Age (years)	<40	0
	40–59	7
	60–69	12
	70–74	15
	75–79	16
	≥80	18
Heart rate (/min)	<40	11
,	40–69	2
	70-119	0
	120–159	4
	≥160	7
Systolic blood pressure (mmHg)	<70	13
e joiene e e e e e e e e e e e e e e e e e e	70–99	5
	100–199	0
	≥200	2
Körpertemperatur (°C)	<39	0
Troipertemperatur (0)	≥39	3
PaO ₂ /FiO ₂ (bei mechanical	<100	11
ventilation or CPAP) (mmHg)	100–199	9
ventuation of of Al / (mining)	≥200	6
Urine output (I/24h)	<0.5	11
Offile output (#24ff)	0.5-0.999	1.
		0
Line of (mondal) [mondal/II]	≥1.0	
Urea (mg/dl) [mmol/l]	<28 [4,6]	0
1 3	≥84 [13,9]	10
Leucocytes (10 ³ /mm ³)	<1.0	12
	1.0–19.9	0
M-1: (≥20	3
Kalium (mmol/l)	<3.0	3
	3.0–4.9	0
N. ((≥5.0	3
Natrium (mmol/l)	<125	5
	125–144	0
	≥145	1
Bicarbonate (mmol/l)	<15	6
	15–19	3
	≥20	0
Bilirubin (mg/dl) [µmol/l]	<4.0 (68.4)	0
	4.0–5.9 (68.4–102.5)	4
	≥6.0 (102.5)	9
Glasgow Coma Score (s page 58)	<6	26
	6–8	13
	9–10	7
Chronic diseases	Metastatic cancer	9
	Hematologic	10
	malignancy	
	AIDS	17
Type of admission	Planned OP	0
	Medical admission	6
	Emergency surgery	8

Reference: Le Gall JR, Lemeshow S, Saulnier F. A new Simplified Acute Physiology Score (SAPS II) based on a European/North American multicentre study. JAMA 1993;270(24):2957–2963.

14.4 Conversion tables

PaO₂/FiO₂ Ratio

The following conversion table is used when blood gas analyzes are not available to determine PaO2 / FiO2:

O₂ Saturation conversion table					
SO ₂ (%)	estimated PaO ₂ (mmHg)				
80	44				
81	45				
82	46				
83	47				
84	49				
85	50				
86	52				
87	53				
88	55				
89	57				
90	60				
91	62				
92	65				
93	69				
94	73				
95	79				
96	86				
97	96				
98	112				
99	145				

FiO₂ on oxygen therapy

Method	O ₂ Flow (I/min)	estimated FiO ₂ (%)
Nasal cannula	1	24
	2	28
	3	32
	4	36
	5	40
	6	44
Nasopharyngeal catheter	4	40
	5	50
	6	60
Face mask	5	40
	6–7	50
	7–8	60
Face mask with reservoir	6	60
	7	70
	8	80
	9	90
	10	95

1.1 Study Objective

To investigate whether the replacement with albumin and the maintenance of its serum level above 30 g/L for 28 days improve survival in the patients with septic shock compared to resuscitation and volume maintenance without albumin.

1.2 Study Design

Randomized Controlled Multicenter

1.3 Protocol Version and Amendments

Final 3.0 from 18JUL2019

2 Analysis Sets

2.1 Full Analysis Set (FAS)

The FAS includes all patients randomized, who have at least one data point after randomization. Patients will be analyzed as randomized (Intention-to Treat, ITT, principle) The primary efficacy analysis will be performed in the FAS. All data assessed will be analyzed in the FAS.

2.2 Per-Protocol Set (PPS)

The Per-Protocol-Set includes all patients of the ITT without additional albumin application other than study medication, who have no *major* protocol deviations.

A protocol deviation is defined as major, if it substantially influences the primary efficacy parameter 90 day mortality.

In particular, application of albumin in addition to the study medication leads to exclusion from PPS, although allowed according study protocol for reasons of patient's safety. Primary efficacy analysis will be repeated in the PPS as a sensitivity analysis.

In case of differences between treatment randomized and applicated, a further sensitivity analysis will be performed "as treated".

2.3 Safety

The safety analysis will be performed for FAS, but patients will be analyzed as treated.

03.04.2017

2.4 Listing Only Set (LOS)

BI03-H-A2 V03

Patients, excluded from FAS (screening failures) will be listed as far as available. Reasons for exclusion/non-inclusion will be analyzed as far as available.

2.5 Predictable Major Protocol Deviations

Application of albumin in addition to the study medication leads to exclusion from PPS, although it is no protocol deviation. It is allowed according study protocol for reasons of patient's safety, but substantially influences the study objective.

3 Study Centers

40-50 Centers. Centers will be listed with number of recruited patients in the statistical report.

4 Study Variables

4.1 Population Characteristics and Baseline Data

- Eligibility and consent
- Age, weight, height, sex, type of admission, residence before admission to ICU and other demographic data
- Diagnoses, comorbidities, data on infection,
- Lactate
- APACHE II-Score, SAPS-II-Score und SOFA-Score
- Treatment application and compliance, albumin application in addition to study medication

4.2 Primary Endpoint

90-day-mortality

4.3 Secondary Endpoints

- 28- and 60-day-mortality
- Mortality rate at ICU and in-hospital mortality
- SOFA score
- Duration of stay on ICU and duration of hospitalization,
- Days not requiring artificial respiration, days without vasopressors
- Assessment of amount of albumin applicated, other colloids and crystalloids
- · Overall fluid intake, overall fluid balance

4.4 Safety Variables

4.4.1 Adverse Events

AEs, SAEs and sepsis related events

4.4.2 Laboratory Parameters

- Microbiology
- Routine laboratory: hemoglobin, creatinine, bilirubin, C-reactive protein, procalcitonin, leukocytes, thrombocytes, lactate, arterial blood gas (paCO2, paO2, FiO2, SO2, pH, ScO2)

4.4.3 Other Safety Data

- Clinical parameters: body temperature, respiratory rate, hemodynamic parameters (SAP, MAP, DAP, CVP, CO)
- Anti-infective therapy
- Adjunctive sepsis therapy
- Intensive care (intubation, central venous catheter, arterial catheter, renal replacement therapy, ventilation, ECMO, hemodynamic monitoring)

5 Handling of Missing Values and Outliers

5.1 Missing Values

Single day missing values in GCS (up to 3 consecutive) will be replaced by LOCF for evaluation of daily SOFA score.

All other missing values will be treated as such and not replaced by estimates. Missing values for the primary efficacy parameter 90 day mortality will be respected in Kaplan Meier analysis of mortality.

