7.1 Screening and 24-h period before randomisation

- Obtaining written informed consent or confirming the urgency of participating in the clinical trial with possible patient benefit by an independent consultant or other procedures established in the trial centre to include patients who are unable to provide informed consent
- Checking the inclusion and exclusion criteria (including pregnancy test (blood or urine) for women of childbearing age)
- Recording the time of onset of septic shock
- Collection of basic data (sex, age, weight, height, time of hospital admission, time of ICU admission, type of admission, referring facility prior to transfer to the ICU, etc.)
- Documentation of primary or secondary admission diagnoses
- Documentation of concomitant diseases present on admission to the ICU
- Collection of data on infection, microbiology and anti-infective therapy
- Collection of raw data for the calculation of APACHE II, SAPS II, and SOFA scores from the routine laboratory requests (not for study purposes) from the 24-h period before randomisation (data from ICU or normal ward) (see Appendix)
- Assessment of concomitant medication (catecholamines, inotropes, diuretics, fluid therapy including transfusion, adjunctive sepsis therapy) from the 24-h period prior to randomization
- Recording of intensive care interventions (intubation (ITN), central venous catheter (CVC), arterial catheter (AC), renal replacement therapy (RRT), ventilation, extracorporeal

membrane oxygenation (ECMO), haemodynamic monitoring during the 24-h period before randomisation

 Recording clinical parameters (body temperature, respiratory haemodynamic parameters (SAP, MAP, DAP, CVP, CO) from the 24-h period before randomisation

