6.6 Primary Analysis

The primary efficacy variable 90 day mortality will be analyzed with a Generalized mixed model with fixed effects SAPS II score, baseline lactate, baseline-albumin-serum value, type of admission (surgical/non-surgical) and treatment group and random effect center; descriptive statistics will be presented. The primary analysis will take place in FAS according to ITT-principle; an additional sensitivity analysis in PPS will be performed. In addition, descriptive analysis of 90-day mortality in subgroups with respect to baseline-lactate, baseline albumin, baseline SOFA, SAPS II und APACHE II will be performed.

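### SAP 5.1 bars replacing missing baseline covariates and no rule scores an incomplete SAPS II, so read literally the primary analysis is complete-covariate rather than FAS

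*SAP*

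**What the plan says.** SAP 5.1 allows one replacement: "Single day missing values in GCS (up to 3 consecutive) will be replaced by LOCF for evaluation of daily SOFA score". It then closes the door on everything else: "All other missing values will be treated as such and not replaced by estimates". For the primary endpoint it adds only that missing 90-day mortality is dealt with in the Kaplan-Meier analysis.

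The primary model in SAP 6.6 has "fixed effects SAPS II score, baseline lactate, baseline-albumin-serum value, type of admission (surgical/non-surgical) and treatment group and random effect center". On the analysis set, SAP 2.1 states: "The FAS includes all patients randomized, who have at least one data point after randomization", and "The primary efficacy analysis will be performed in the FAS". Covariate completeness is not a condition for entering the FAS.

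Under Protocol 7.1, the raw data for SAPS II come "from the routine laboratory requests (not for study purposes) from the 24-h period before randomisation". The scoring table in Protocol 14.3 has 15 items and no instruction for an item that was not measured.

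Baseline albumin has different timing. Protocol 7.3 has the sample drawn within 2 hours after randomisation in both groups, and the trial is open-label.

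**The concern.** These statements do not fit together. If a covariate is missing and may not be replaced, an ordinary mixed-model fit cannot use that patient, even when day-90 status is known. The analysis labelled FAS then covers only patients with complete covariates.

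SAPS II is the exposed covariate. It needs many inputs, and these depend on what was ordered for routine care before randomisation. Lactate is an eligibility criterion and a stratification factor, so it should rarely be missing. SAPS II and baseline albumin are also in the protocol's version of the model (Protocol 11.3.2), so the point does not depend on which model is used.

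Two things are at stake: patients lost from the primary test in spite of a known outcome, and a scoring decision left open until the data are visible in an unblinded trial.

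**Working it through.** **1. Do other provisions fill the gap?**
- Protocol 11.3.2 takes the last available baseline value. That needs a value to exist.
- Protocol 9.6 queries missing data. A query cannot recover a test that was never done.
- Protocol 14.4 converts oxygen saturation to PaO2. That serves only the PaO2/FiO2 item, which in SAPS II is scored under ventilation or CPAP.
- Protocol 11.3.2 has multiple imputation, but only for missing 90-day mortality, only as a sensitivity analysis, and only above 10% missing. The SAP does not mention it.
- SAP 5.3 norms values from other time frames to 24 h. The rule stands under fluid intake and output, so its use for the SAPS II urine item (scored in l/24 h) is unclear.

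None of these supplies a value for an unmeasured urea, leucocyte count, potassium, sodium, bicarbonate or bilirubin.

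**2. The plan's sample size (Protocol 11.1).** Inputs: control 50%, albumin 42.5%, two-sided 0.05, power 80%.

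n per arm = [1.960·√(2·0.4625·0.5375) + 0.8416·√(0.25 + 0.244375)]² / 0.075²
= (1.960·0.7051 + 0.8416·0.7031)² / 0.005625 = 693, so 1386 in total, or 1438 with continuity correction.

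The stated 1412 lies between. A Mantel-Haenszel simulation with the protocol's centre assumptions (50 centres, control 40–60%, relative reduction 12–18%, 20,000 runs) gives power 0.799 at 1412. Dropout: 1412 / 0.85 = 1661.2, so 1662. Both stated figures reproduce. (The synopsis gives 42% for the albumin group, which yields 1218 by the same formula. The 42.5% of section 11.1 is used here.)

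**3. Power if patients with a missing covariate are left out.** The loss rates are assumptions, because the documents give none.

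Power = Φ{[0.075·√n − 1.960·0.7051] / 0.7031}, with n per arm = 706·(1 − loss).

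| Lost | n per arm | Analysed | Power | Randomised to keep 1412 |
|---|---|---|---|---|
| 0 | 706 | 1412 | 0.807 | 1662 |
| 2% | 692 | 1384 | 0.800 | 1696 |
| 5% | 671 | 1342 | 0.787 | 1750 |
| 10% | 635 | 1270 | 0.765 | 1846 |

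The last column is 1412 / (1 − loss) / 0.85, rounded up at each step. Mantel-Haenszel simulation (8,000 runs each) gives 0.77 at 5% and 0.75 at 10%, slightly lower than the formula.

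**4. What item-level rates would produce such losses?** For the six SAPS II blood items named in step 1, with independent missingness q per item, the share with at least one missing is 1 − (1 − q)⁶. That is 3.0% at q = 0.5%, 5.9% at 1% and 11.4% at 2%. Items drawn together tend to be missing together, which lowers these figures.

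**5. Is the loss already budgeted?** Protocol 11.1 builds the 15% from loss to follow-up, refusal on regaining capacity, and missing consent from representatives. Missing covariates are not listed.

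**The case against.** The strongest case against is that this is a silence rather than a stated exclusion, with no evidence that it matters much. Several stronger readings are tempting, and the documents do not support them.

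- *A reader might infer that one unmeasured item voids the whole SAPS II.* No passage says so. Scoring an unmeasured item as normal could be seen as part of deriving the score rather than as replacement by an estimate. Dropping the patient is likewise default software behaviour, not a written rule. This stands. The literal reading leads to exclusion, but it is a reading.
- *A reader might infer that urea, sodium, potassium and bicarbonate are not collected, because the routine laboratory list in Protocol 1.6 and 7.2 omits them.* That list is a separate item. The schedule has its own row for SAPS II and APACHE II data, and Protocol 7.1 asks for the raw data. The omission is weak evidence of missingness.
- *A reader might infer a loss of 10% or 20%.* Such figures need assumed, independent missingness across many items, including bedside values that will rarely be absent in ICU patients on vasopressors. Real loss could be negligible.
- *A reader might infer a biased treatment comparison.* For items fixed before randomisation, exclusion is expected to be unrelated to arm. The cost is in precision and representativeness. That recent arrivals or ward patients would be lost most often is plausible but not documented.

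Protocol 11.1 also calls the sample size conservative for the planned mixed model, which may absorb a small loss.

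What survives is the written bar on replacement. It is a rule, it covers every covariate in the primary model, and it works against analysing the whole FAS. Baseline albumin is a partial exception to the last bullet. It may be sampled after open-label allocation, and Protocol 6.3.1 requires the sample before the first albumin dose, a step that the control group does not have. Its missingness could therefore differ by arm, though nothing in the documents shows that it will.

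**Conclusion.** The point holds in limited form. SAP 5.1 prohibits replacement, and no rule covers an incomplete SAPS II. Taken literally with SAP 6.6, this turns the FAS primary analysis into a complete-covariate analysis and leaves out patients whose day-90 status is known.

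The size is unknown. A 2% loss leaves power at about 0.80. Losses of 5% and 10% bring it to about 0.79 and 0.765, beyond the 15% dropout allowance. These figures assume 1412 patients with known outcome, equal loss in both arms, rates of 50% and 42.5%, and no gain from covariate adjustment. The case for change rests mainly on keeping the randomised set and fixing the rule in advance, and less on the power figures.

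**What to change.** Amend SAP 5.1 before database lock:

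1. Exempt the baseline covariates of the primary model from the no-replacement rule.
2. Score an unmeasured SAPS II item as 0 points. Norm urine observed for less than 24 h by the SAP 5.3 rule, and state that the rule applies to SAPS II.
3. Replace any other missing pre-randomisation covariate by the overall mean, pooled over arms, plus a missing indicator.
4. For baseline albumin use the pooled mean without an indicator, because its missingness may arise after allocation. Report that missingness by arm.
5. Keep every FAS patient with known day-90 status in the primary model, and run the complete-covariate analysis as a sensitivity analysis.

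Other prespecified methods could also serve. What matters is that one is written down and that patients with a known outcome are kept. The cost is SAP wording and a few lines of code, with no new data. The downside is that SAPS II is slightly understated in patients with unmeasured items. As these items precede randomisation, this should not distort the treatment contrast.

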5.2 Outliers

No special procedures for outliers are planned.

6.1 Sample Size Considerations

1412 evaluable patients, 706 per arm planned. For details of sample size planning see study protocol.

6.2 General Principles

All available data will be analyzed at least descriptively. Descriptive analysis includes at least number of available and missing data, mean, standard deviation, minimum, quartiles including median and maximum for metric data and number and % of patients per category for non-metric data. Day-wise descriptive statistics will include at least number of available data, mean, minimum, median and maximum

All analyses will be performed by treatment group and in total.

6.3 Population Characteristics and Baseline Data

Descriptive analysis

6.4 Previous and Concomitant Diseases and Therapies

Frequency analysis

6.5 Exposition to Therapy / Compliance

Descriptive analysis

6.6 Primary Analysis

The primary efficacy variable 90 day mortality will be analyzed with a Generalized mixed model with fixed effects SAPS II score, baseline lactate, baseline-albumin-serum value, type of admission (surgical/non-surgical) and treatment group and random effect center; descriptive statistics will be presented. The primary analysis will take place in FAS according to ITT-principle; an additional sensitivity analysis in PPS will be performed. In addition, descriptive analysis of 90-day mortality in subgroups with respect to baseline-lactate, baseline albumin, baseline SOFA, SAPS II und APACHE II will be performed.

6.7 Secondary Analyses

28- and 60-day-mortality, mortality rate at ICU and in-hospital mortality will be analyzed descriptively. Overall mortality will be described by Kaplan Meier methods.

SOFA score will be analyzed descriptively over time, for organ subscores frequency analysis will be presented. Number and % of patients with organ dysfunction defined as any subscore > 2 and number of patients with organ failure defined as any subscore >3 will be given. Duration of stay on ICU and duration of hospitalization, days not requiring artificial respiration

and days without vasopressors will be analyzed descriptively.

Amount of albumin applicated, other colloids and crystalloids will be analyzed descriptively over time.

Overall fluid intake and overall fluid balance will be analyzed descriptively over time. Definition [1] for overall fluid output will be used, if 90% of perspiration values are given If perspiration is missing in more than 10% of visits n patients, definition [2] excluding perspiration will be used for main analysis. Analysis in subgroup with perspiration available will be performed as additional sensitivity analysis.

6.8 Safety and Tolerability Analyses

6.8.1 Adverse Events

For sepsis related AEs, frequency analysis with respect to categories cardiovascular / respiratory / hepatic / renal / hematological / neurological, will be presented.

Respective entries of AEs possibly related to study medication in AE data base will be selected and presented separately.

All AEs and serious AEs will be presented by incidence analysis of the pre-specified categories as well as intensity, relationship to study medication, measures with respect to study medication as well as other measures and outcome. Events of category "Other" will be listed.

For infections, frequency analysis over types, grade and origin will be provided. Analysis of daily assessed data will be performed over the following time frames: Screening / 6h after randomization / Day 1 / Day 2-7 / Day 8-28.

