- Haematological event: e.g., coagulopathy, DIC, thrombocytopaenia, thrombocytosis
- Neurological event: e.g., delirium, confusion

Each sepsis-related clinical event must be documented in the eCRF during the respective visit with specific parameters. The investigator assesses the sepsis-related clinical event in ZKSJ0112 ARISS

Zentrum für Klinische Studien

terms of an association with the trial drug and classifies it as "possible" or "not possible". Documentation of the sepsis-related clinical event as an AE occurs only if the examiner suspects a connection with the administration of the trial drug, which is therefore only possible in the albumin group.

However, the following effects of the trial drug may be substance-specific and must be documented as AE:

- Flush
- Urticaria
- Fever
- Nausea
- Anaphylactic shock
- Hypervolaemia
- Pulmonary oedema
- Transmission of infection (in addition to sepsis, see corresponding section of the valid information brochure).

Clinically relevant worsening of a pre-existing disease not related to sepsis should be considered and documented as an AE.

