- Total amount of fluid administration in the ICU (individual average amount of fluids given enterally or parentrally, including volume therapy) and total fluid balance in the ICU (individual average difference between daily fluid administration urinary output and other fluid loss): descriptive statistics, especially quartiles.

All secondary endpoints, unless included in the primary analysis model, will be exploratively compared using appropriate parametric and nonparametric tests between treatment groups.

Health economics:

In the context of the ARISS study, a health economic cost-benefit analysis of volume replacement therapy of the ICU stay will be carried out up to a maximum of day 28. The direct costs of colloid, crystalloid and albumin administration will be recorded and the length of stay (first hospitalisation and stay since study participation) evaluated economically to assess whether albumin administration has an effect on hospital costs or not. At the patient level, DEALE (declining exponential approximation of life expectancy) (27) will be applied to calculate patient-specific life expectancy based on mortality rates in the general population and in the disease-specific population. The subsequent cost-effectiveness analysis will yield the cost per year of life for albumin administration. The robustness of the analysis will be checked with one-way and multi-way analyses as well as probabilistic sensitivity analysis.

Analysis of safety parameters:

Frequencies of AEs and SAEs will be analysed using frequency tables. In addition, frequencies of selected AEs (sepsis-related clinical events) will be analysed.

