6.11 Deviation from Protocol and Amendment

Corresponding to recommendations of reviewers, subgroups with respect to SOFA, SAPS II and APACHE II baseline values are prespecified instead of using quartiles.

7 Software and Validation

Analysis will be performed with SAS Version 9.4 or higher.

Validation plan:

All programs will be validated on either a basic or an enhanced validation level. Basic validation level means validation by the programmer according ZKS Jena SOP Bi06 and includes check of program code, check of log-file and check of output. Enhanced validation will be performed by an independent programmer and includes enhanced check of program code, log-file and output. Primary efficacy analysis will be validated by independent duplicate programming. Results of adverse events analysis will be cross-checked with the contents of the safety data base.

Programms for DSUR and SMC reports will be validated on basic validation level by the respective programmer.

Analysis	Validation level
Population characteristics and baseline data	basic
Previous and concomitant diseases and therapies	basic
Exposition to therapy / compliance	basic
Primary analysis	enhanced
Secondary analyses	basic
Adverse events	basic
Laboratory parameters	basic
Other safety data	basic

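### SAP 6.8.1 plans only a listing for 'Other' adverse events, with no coding and no incidence by event term and arm, so an excess of one specific unanticipated event would not be tabulated

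*SAP*

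**What the plan says.** **SAP.** Section 6.8.1 sets the rule for the AE section of the database: "All AEs and serious AEs will be presented by incidence analysis of the pre-specified categories as well as intensity, relationship to study medication". It adds the measures taken and the outcome, and then provides for the remainder: "Events of category 'Other' will be listed". The categories are not enumerated. Sepsis-related events are handled separately: "frequency analysis with respect to categories cardiovascular / respiratory / hepatic / renal / hematological / neurological, will be presented". Two general rules apply to all of this. Section 6.2 says "All analyses will be performed by treatment group and in total", and section 2.3 says "The safety analysis will be performed for FAS, but patients will be analyzed as treated".

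**Protocol.** Section 11.3.2 states: "Frequencies of AEs and SAEs will be analysed using frequency tables". It does not confine those tables to named categories. Section 3.2 counts the occurrence of AEs and SAEs among the secondary endpoints, and section 11.3.2 plans exploratory between-group tests for secondary endpoints. The only list of specific AE terms is in section 8.2, introduced by "the following effects of the trial drug may be substance-specific and must be documented as AE": flush, urticaria, fever, nausea, anaphylactic shock, hypervolaemia, pulmonary oedema and transmitted infection. The same section also requires clinically relevant worsening of a pre-existing disease unrelated to sepsis to be recorded as an AE.

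**Declared departures.** SAP 6.11 names one change from the protocol: "subgroups with respect to SOFA, SAPS II and APACHE II baseline values are prespecified instead of using quartiles". It does not mention adverse events.

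**The concern.** A listing shows each event on its own line. It gives no number of patients, no percentage and no denominator, and without coding the same event can appear under several free-text names. Unforeseen events are the ones least likely to have a category prepared for them. Worsening of a comorbid disease, which the protocol requires to be recorded, matches none of the eight terms in protocol 8.2. A stroke or gut ischaemia not attributed to sepsis would be in the same position.

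A randomised comparison with a planned 831 patients per arm is a good opportunity to notice a harm that nobody expected. If one event type is more frequent under albumin, the reader of the report should be able to see it in a table. Under the rule as written, the reader would have to find and count the lines.

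**Working it through.** No figure in the plan is in dispute, so there is none to reproduce. The check is a reading of the sections against each other, followed by an illustration of scale.

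**Step 1. What each planned output can show about an event in 'Other'.**

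- *Incidence by category:* at most one pooled 'Other' row. The SAP does not say whether that row exists.
- *Intensity, measures and outcome:* these cover all AEs and SAEs and, through SAP 6.2, are given by arm. They are not described by event term, so an excess of one event type is mixed with every other event.
- *Relationship to study medication and action on the drug:* controls receive no trial drug, so there is no meaningful control comparison. Relationship is judged with the allocation known (open label, protocol 11.2).
- *Sepsis-related organ categories:* by arm, but only for events judged explainable by sepsis.
- *Laboratory values, SOFA, mortality:* by arm, but they do not identify which clinical event is in excess.
- *Listing:* shows the event itself, without counts by arm.

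No output described gives the number of patients with a specified 'Other' event by arm.

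**Step 2. Scale under assumed rates.** The documents give no rate for any unlisted event, so the rates below are assumptions. The 831 per arm is the planned number randomised (protocol 1.1).

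For 2% versus 4%:

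- Expected patients: 0.02 × 831 = 16.6 and 0.04 × 831 = 33.2.
- SE of the difference: √[(0.02 × 0.98 + 0.04 × 0.96)/831] = √(0.058/831) = 0.00835.
- 95% CI: 0.02 ± 1.96 × 0.00835 = 0.0036 to 0.0364.
- Power at nominal two-sided 0.05: the pooled null SE is √(2 × 0.03 × 0.97/831) = 0.00837. Then (0.02 − 1.96 × 0.00837)/0.00835 = 0.43, which gives about 67%.

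The same formulas over a range of assumed rates:

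| Control vs albumin | Expected patients, 831 per arm | Difference in points (95% CI) | Power, 831 per arm | Power, 706 per arm |
|---|---|---|---|---|
| 0.5% vs 2% | 4 vs 17 | 1.5 (0.4 to 2.6) | 79% | 72% |
| 1% vs 3% | 8 vs 25 | 2.0 (0.7 to 3.3) | 83% | 77% |
| 2% vs 4% | 17 vs 33 | 2.0 (0.4 to 3.6) | 67% | 60% |
| 5% vs 8% | 42 vs 66 | 3.0 (0.6 to 5.4) | 70% | 63% |

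The powers refer to a single event type with no allowance for multiplicity. They show only that excesses of this order would often be visible in a table by term and arm. They do not predict that any such excess exists.

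**Step 3. Observation windows.** Protocol 8.3 records AEs in the albumin group until 24 hours after the last dose, and in controls until day 28 or earlier ICU discharge. Any crude percentage by arm, in the tables already planned or in those proposed here, rests on windows that can differ between the arms.

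**The case against.** The strongest reply is that the SAP already compares all adverse events by arm. A reader might infer from the listing sentence that an unanticipated harm of albumin would never be compared between arms, or would go uncounted. The documents do not support that. SAP 6.2 applies to every analysis, and SAP 6.8.1 extends the intensity, relationship, measures and outcome summaries to all AEs and SAEs, which on its wording includes 'Other'. An overall excess of severe or fatal events could show there, and organ events, laboratory data and mortality are also given by group. This part of the reply stands.

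Four further points also limit the concern:

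- The categories may be broader than the eight terms in protocol 8.2. They may be set in the CRF, which is not available, and 'Other' may be a pooled row. It therefore cannot be said that the tables cover only known product reactions. Hypervolaemia and pulmonary oedema, for instance, are in protocol 8.2 but not in the product-brochure list of protocol 6.5.
- Some arrhythmia or bleeding events could fall into the sepsis organ categories, whose definitions mostly give open examples.
- A reader might call this an undeclared departure from the protocol. The protocol promises frequency tables but not coding or tables by term, and incidence by category is a frequency table. The SAP is less specific than the protocol suggests, but a breach is not shown.
- Coding may be defined in the SAE Manual cited in protocol 8.6.2. Each SAE receives a second assessment, and the safety committee receives all safety data (protocol 8.9).

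None of these supplies incidence by term and arm in the SAP. Pooled summaries dilute an excess of one event type, and safety oversight during the trial does not replace a table in the final report.

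**Conclusion.** The point holds in a limited form. For events outside the pre-specified categories, the plan describes a listing but no coding and no incidence by term and arm. An excess of one specific unanticipated AE or SAE would not be tabulated, although pooled by-arm summaries could reveal an overall excess.

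The number of events affected cannot be determined from the documents. The 17 versus 33 patients at 2% versus 4% are an illustration under assumed rates and the full planned 831 per arm. The conclusion assumes that no coding or term-level table is specified in a document not seen here. It does not touch the primary analysis. It is a cheap improvement to safety reporting and should be made.

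**What to change.** In SAP 6.8.1, replace the listing sentence with a rule that:

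1. Enumerates the pre-specified categories.
2. Codes every AE and SAE, including 'Other', with a named standard dictionary by organ class and term.
3. Reports by arm the number and percentage of patients with at least one event, and the number of events, for total AEs, total SAEs, and each organ class and term.
4. States with these tables the observation window or time at risk in each arm, because protocol 8.3 ends recording differently in the two groups.
5. Keeps apart the sepsis-type events entered as AEs because of a suspected drug connection. SAP 6.8.1 already plans to present these separately, and protocol 8.2 makes them possible only in the albumin group.
6. Retains the listing as a supplement and uses the same tables for the safety committee and annual safety reports.

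The cost is the time to code free-text events and a longer table with many small counts, which should be read descriptively. Trial conduct and data collection do not change.
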